The CAB reviewed potential evidence-based PEIs to adapt. They identified a brief, indicated PEI program for adaption, which is aimed at reducing youth anxiety and stress.^{21,33} They indicated its brevity and potential for youth engagement (board games, playing cards) as appealing. Moreover, it was designed using a CBPR approach and successfully adapted for Latinx youth. There is evidence supporting its feasibility, fidelity, and acceptability with non-Native youth and shown promise in reducing anxiety.^{21,33} It is grounded in cognitive-behavioral and emotional theories of anxiety and stress^{34,35} and aims to improve emotion awareness and expression, reduce cognitive biases, and enhance self-efficacy to manage anxious or stressful situations. It uses streamlined cognitive, behavior, and social skills training using a 12-page manual, active learning (role-playing, games), and brief 30-minute sessions. Training is also minimal at 5 hours plus two 30-minute feedback sessions.

The PEI program^{21,33} is delivered across six weeks with 20-30 min weekly sessions. Youth engage in games and role-play reducing anxiety and stress in mildly challenging situations to provide in-vivo exposure. Session 1 involves introductions, guided relaxation training by

listening to a audio-recording, and learning about different types of emotions using playing cards with characters who display facial emotional expressions. Session 2 teaches youth about worries and how to handle them using a group board game. Session 3 focuses on having conversations with others through guided practice using a role-playing format revolving around different scenarios with the youth. Session 4 teaches youth how to be assertive through guided practice using a role-playing format revolving around different scenarios with the youth. The CAB identified this as an area of adaptation in initial meetings due to the lesson focusing on looking a person in the eye. Session 5 teaches youth how to face their fears by roleplaying mildly fearful situations and learning how to make themselves less scared. Session 6 is a review session. Parents and teachers are sent notes of what youth learned in each session and asked to encourage youth to practice their learned skills.

Purpose of the Study

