The purpose of this study was to build upon our community-based participatory research (CBPR) partnerships with the [tribal name] tribal community to culturally adapt an evidence-based, indicated PEI program for universal delivery with 8-12-year-olds living on the [tribal name] Reservation using a systemic, theory- and culturally-grounded qualitative approach. In addition, we will use a mixed methods approach to evaluate the feasibility of delivering the adapted PEI in two tribe-serving schools and estimated effect sizes of changes in anxiety and depression from pre- to post-intervention using single-group design (i.e., no control group). We also aimed to determine the extent to which the program was acceptable and enjoyable for [tribal name] youth.

Research Design

Our study involved two major phases:

- 1) a qualitative phase, which included collaboration between the CAB and research team that resulted in a conceptual framework for cultural adaption of the PEI program, gathering suggestions for cultural adaptations and to improve the PEI program from focus groups with key adult stakeholders in the [tribal name] community (Elders, parents, teachers, and mental health specialists) and youth stakeholders, and the CAB making cultural adaptions to the PEI program based on the focus group data.
- 2) a clinical trial phase, which included delivery of the adapted intervention in two tribal serving schools for the [tribal community name] Reservation using a pre-post, single group design (i.e., no control group). We evaluated feasibility and acceptability using youth and provider self-report data and estimated the effect sizes of changes in youth anxiety and depressive disorder symptoms using youth and teacher reports. In addition, we gathered survey data on youth resilience, anxiety control beliefs, and rumination.

Cultural Adaptation of the PEI Program (Phase 1)

Development of Conceptual Framework and Review of the PEI program (Step 1)

In Year 1, the 8-10 member CAB (Elders, parents, teachers, mental health professionals, cultural experts) and research team met once a month and engaged in several activities throughout Step 1 described in this section and Step 3 described in a later section. All CAB members completed a

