At the end of Year 2, the CAB and research team met to review all grouped suggestions gathered from the WGs and FGs. The CAB identified and integrated modifications or additions to our conceptual framework if needed based on the FG feedback. Next, the CAB reviewed the content, format, and learning objectives of each of the six PEI program modules and training protocol within the context of this finalized conceptual model. Specifically, the CAB identified the type of change needed (e.g., content, language, learning strategy), amount of change required (no change, small change, moderate change, large change), and barriers (timeline/budget). The CAB decided on the importance of the change (essential or non-essential), made final decisions on adaptations, and the physical adaptations of the PEI program materials were made by the developers of PEI as requested by the CAB.

Adapted PEI Program Intervention Evaluation (Phase 2; Clinical Trial)

In Year 3, The CAB worked with the research team to culturally adapt the intervention and identified two school counselors (i.e., an American Indian tribal member and a white non-tribal member) to provide it in the schools. Both providers completed the modified PEI program training based on CAB decisions for adaptation and the CITI Training (through Montana State University-Bozeman) before working with youth in the school. They also completed a background check for each school. Providers recorded youth attendance, dropout of the intervention, and completed the Brief Reactions Form for after each session.

In Year 3, we recruited 28 Native youth ages 8-12 years-old from the [two tribal serving school names] (15 youth per school) to participate in the adapted PEI program. The adapted PEI program was delivered to a group of 3-5 youths at one time with three groups participating in each school. Written informed consent was obtained from the parents or legal guardians before youth participated in the intervention or complete pre- and post-survey assessments. Youth participants also provided written assent before completing the pre-intervention and post-intervention surveys or participating in the adapted PEI program.

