Youth participants completed the pre-intervention survey (~30 minutes to complete based on our pilot study) one week before session 1 and the post-intervention survey one week after session 6 of the adapted PEI program. The post-adaptation usability survey was administered at the end of each session. Youth completed the survey using paper and pencil. The research team explained the purpose of the study and intervention. They also read the assent form out loud to youth and answered any questions youth had about the study. Those youth who verbally agreed and checked “yes” on the assent form completed the youth survey and participated in the intervention. Youth who choose not to participate in the study returned to their classroom. All youth were notified of their right to withdraw the study and intervention at any time without consequence. The research team helped youth who may have difficulty comprehending items or response options.

Youth Assessments. The CAB reviewed and approved the following instruments as being culturally appropriate (minor changes were made to existing measures) for our previous study

with 71 Native 8-13-years-old at the [tribal school name]. Each measure showed acceptable to excellent reliability and both convergent and discriminant validity with other established measures in that study (Scott, [name], Small, & McCullen, 2023).

Youth Demographics. We asked children to provide personal information including gender, age, ethnicity, tribal affiliation, grade level, and family structure.

Revised Child Anxiety and Depression Scales – Short Child Version (RCADS-SC).^{37,38} The RCADS-SC is a 25-item self-report instrument used to assess DSM-IV criteria (APA, 1994) of symptoms for anxiety disorders (excluding Posttraumatic Stress Disorder and Specific Phobias) and depression. We asked the children to rate how often each anxiety and depression symptom is true of them on a rating scale consisting of: 1 (Never), 2 (Sometimes), 3 (Often), and 4 (Always). Higher scores represent the experience of more anxiety and depression symptoms as based upon the DSM-IV criteria.

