- G. Possible Exposure to COVID19 Safeguards. There is a slight risk for exposure to COVID19 due to the group nature of the study. We will ensure that all groups are held in a location that allows for proper airflow, social distancing, and that all participants wear masks or a protective shield. This will be stated in the consent form and the project manager will inform all potential participants upon scheduling the work/focus group or planning the intervention in the schools. We will use a COVID19 screening tool that [name] has successfully used in his lab at MSU to collect physiological data from human participants in small spaces.

3. Response Procedures for Adverse Events

- A. Discomfort with Disclosure. All study personnel will respond to participants in a compassionate, caring, and professional manner when feelings of uncomfortableness or embarrassment arise. Adult participants who experience these feelings will be referred to tribal health and youth will be referred to the school counselor, who will then make the

decision to control tribal health and the parents/legal guardians. All participants will be encouraged to reach out to the research team if a late adverse reaction occurs and will be given specific written and verbal instructions on how to do so during the informed consent and assent explanation.

B. Mandatory Reporting. Participant reports of physical abuse and neglect or the threat of imminent physical harm to oneself or others is required to be reported to the proper authorities. Each school has its own procedure for handling these types of reports and in anticipation of the possible risk of such disclosures, we have established our procedures to coincide with the schools. In addition, we have established our own procedures for the work/focus groups that are not held within the school system.

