The MSU Office for Research Compliance is responsible for the general oversight of all grant activities and will inform [name] (PL) about changes and requirements for the DSMP. Moreover, we will appoint an independent three-member Data and Safety Monitoring Board

(DSMB) to provide ongoing oversight of the study. We will have an expert in behavioral intervention science, a statistician with expertise in evaluating behavioral interventions using mixed method designs, and a researcher with expertise behavioral interventions with Native American youth. Meetings will occur semi-annually by telephone or WebEx, and unless closed by the Chair, will be joined by [name] (PL), [project manager name] (Project Manager), and one of the CAB members.

The DSMB responsibilities will include monitoring and evaluation of the following:

- A. the study protocols, materials (e.g., consent and assent forms; measures) and plans for data and safety monitoring
- B. study progress with respect to participant recruitment, accrual and retention, follow-up and protocol adherence
- C. participant safety in regard to adverse events and other safety issues, including recommendations to terminate the study due to safety concerns (if necessary)
- D. maintaining the confidentiality and quality of the study data
- E. ongoing risks and benefits to participants throughout the study

The research team will update the general Data and Safety Monitoring Plan procedures as needed. We will report adverse events to the [tribal name], participating tribe-serving schools, and the IRBs annually. In terms of serious adverse events, we will report them immediately to these entities, CAIRHE, NIH, and the DSMB. We will submit a written report within 3 days of the event serious adverse event occurring and the report will be in a format stipulated by the [tribal name], schools, and IRB. It will contain information pertaining to the date of the event, description of the event, assessment of the cause, whether the event indicates an increased risk for current or future participants in the study, and whether changes to the informed consent or study protocol is needed.

STATISTICAL ANALYSIS PLAN FOR PHASE 2 (CLINICAL TRIAL)

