Study Aim 2: Evaluate the feasibility and acceptability of the culturally adapted PEI program. We calculated the frequency of youth attendance rates across sessions, dropout rates, and survey response rates. We also created tabular summaries of the Likert scale ratings from the usability survey and proportion of respondents who rated each module or all modules on average as 2 or 3. A module or the entire program was successfully adapted if at least 80% of youth rated it as a 2 or 3 on the Likert scale for acceptability and enjoyability.

Study Aim 3. Estimate effect size changes in anxiety and depressive symptoms in [tribal name] youth. Primary outcomes of interest for a future efficacy trial will be changes in the RCADS-S scales. For each scale, we computed the change in the scale score from baseline to post-intervention (post – pre) and computed unadjusted averages and standard deviations. A one-sample t-test of the changes in any response scale will have 80% power to detect a standardized effect size (Cohen's d) of at least 0.53, and 90% power to detect an effect size of at least 0.61. We will also obtain adjusted estimates using mixed effects linear regression models of post-test score on pre-test score with demographic factors and random effects for school and intervention group nested within school. This will allow us to estimate intra-class correlations for intervention group and schools, which will be required for sample size estimation in a full efficacy trial.

INSTITUTIONAL REVIEW BOARD AMENDMENTS

The following pages (not numbered, but in order of date) contain tribal college IRB amendments that were submitted and approved throughout the study period.

February 9, 2021

Dear [tribal college] IRB,

We are requesting a minor modification for the approved study titled, "A Native Path to Courage." We have outlined the modification below.

- 1) We plan on using a professional online transcription service (Rev.com) to transcribe work and focus group data. The company uses state-of-the-art encryption procedures for audio files to be uploaded and all professional transcribers are required to sign nondisclosure and confidentiality agreements (<https://www.rev.com/enterprise/security>). In addition, we can request for all audio files to be removed from their servers after transcription is complete. We will remove names from the transcription documents upon receipt. Only first names are mentioned in the audio recordings.

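### The documents describe no systematic question to children or parents about adverse reactions to the sessions, and the SAP has no adverse-event summary, so an absence of reports would be weak evidence

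*Combined protocol and SAP*

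**What the plan says.** DSMP section 3.A (Discomfort with Disclosure) sets the rule for reactions that surface later: "All participants will be encouraged to reach out to the research team if a late adverse reaction occurs". Instructions on how to do so are given at consent and assent. No check-in and no time window are described.

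Other parts of the documents add routes by which a problem could come to light:

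- **DSMP section 2:** a form on which the research team records problems, concerns about participants and unusual events during groups, sessions and survey collection.
- **DSMP 2.E:** training of all team members in recognising adverse events.
- **DSMP 2.B:** a notice to the school counselor when a child's post-intervention RCADS T-score exceeds 70.
- **Teacher Assessments:** homeroom teachers' RCADS ratings.
- **Post-Intervention Acceptability Focus Groups and Interviews:** youth focus groups on the last day, then interviews with 3-4 youth across each school, 4 parents, 4 teachers and both providers.

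Children also fill in a form at every session: "The post-adaptation usability survey was administered at the end of each session". Its described content is how well the module was liked, learned and accepted, its perceived effect and its cultural fit.

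DSMP section 5 makes the DSMB responsible for monitoring "participant safety in regard to adverse events and other safety issues". The SAP's feasibility outputs under Study Aim 2 are these: "We calculated the frequency of youth attendance rates across sessions, dropout rates, and survey response rates", together with usability ratings. Study Aim 3 covers RCADS change and intra-class correlations. Neither aim mentions adverse events.

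**The concern.** The participants are 8 to 12 years old, and session 5 has them role-play mildly frightening situations. A child upset by a session may show it only at home, where staff do not see it. Under the described plan that reaction reaches the team only if the child or a parent volunteers it, or if it shows indirectly in a later symptom score or interview.

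The DSMP's list of potential adverse events ties discomfort to groups and surveys, and does not list worsening of symptoms. So even the routes that exist are not pointed at reactions to the sessions. A plan that does not ask, in a sample this small, will probably produce few or no reports. The risk is that the next trial inherits a blank record without anyone being able to say what it is worth.

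**Working it through.** **Inputs.** The Phase 2 section gives the number of children: "In Year 3, we recruited 28 Native youth ages 8-12 years-old". The same sentence gives 15 per school, which for two schools makes 30, so both are carried. The design is a single group, so there is no comparator for event rates. The documents give no reaction rate and no capture share; both are assumptions below.

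**The plan's own figure.** None concerns safety. The only sample-size statement is the power of the one-sample t-test in Study Aim 3 (80% at d = 0.53, 90% at d = 0.61). Assuming two-sided alpha of 0.05, an exact t-test calculation gives 80.1% and 89.8% at n = 30, and 77.1% and 87.5% at n = 28. The stated power thus reproduces at 30. It bears on this point only in showing that the denominator needs settling.

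**Step 1: what zero events would mean with full capture.** The one-sided 95% upper bound solves (1 − p)^n = 0.05:

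- n = 28: 1 − 0.05^(1/28) = 10.1%
- n = 30: 1 − 0.05^(1/30) = 9.5%
- Two-sided exact (Clopper-Pearson) upper limit, n = 28: 1 − 0.025^(1/28) = 12.3%

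Excluding a 5% rate with zero events would take 59 children (ln 0.05 / ln 0.95, rounded up).

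**Step 2: incomplete capture.** If a share c of reactions is recorded, the data bound p × c, so the bound on p is 10.1% / c (unrounded 10.15%):

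| Capture c (assumed) | One-sided 95% bound on true rate, 0 of 28 |
|---|---|
| 100% | 10.1% |
| 75% | 13.5% |
| 50% | 20.3% |
| 25% | 40.6% |

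**Step 3: chance of a blank record.** P(no reports) = (1 − p × c)^28:

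| True rate p (assumed) | c = 100% | c = 50% | c = 25% |
|---|---|---|---|
| 5% | 24% | 49% | 70% |
| 10% | 5% | 24% | 49% |

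These figures treat children as independent. They were taught in three groups per school; if reactions cluster by group, the bounds widen.

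**Step 4: does any existing route amount to asking?**

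- The staff form and training depend on what is noticed at study contacts.
- The T-score notice comes once, after the programme. It is not linked to adverse-event reporting and misses worsening that stays below the cut-off.
- Teachers rate symptoms, not reactions to sessions, and the SAP summarises mean change, not the number of children who worsened.
- The described focus-group and interview topics are experience and improvement, and the interviews reach only a subset.
- The provider form covers delivery, usefulness, understanding and participation.

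**The case against.** The strongest reply is that the plan has more safety machinery than section 3.A suggests. The two providers are school counselors who see the children weekly and complete a form after each session. Staff log concerns, which are discussed at regular meetings. Adverse events go to the DSMB, the IRBs and the schools under the DSMP, which is a legitimate place for them in an SAP confined to Aims 2 and 3. Section 3.A itself concerns embarrassment and discomfort, covers adults in work groups too, and is not offered as the method for finding reactions to sessions.

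Much of this stands, and it rules out several stronger readings:

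- A reader might infer that late reactions can be captured only through participant contact. The routes above contradict that.
- A reader might infer that the DSMB would have reports without a denominator. DSMP section 5 also gives it recruitment, accrual and retention to monitor.
- A reader might infer that the plan treats a clean record as proof of safety. It sets no safety endpoint and draws no such conclusion.
- A reader might say outright that nobody asks. The usability survey, interview questions and provider form were attachments and are not in the text, so the supportable statement is that no such question is described.

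Two further limits apply. The sentence "Parents and teachers are sent notes of what youth learned in each session" belongs to the account of the programme before adaptation, so a return slip on those notes cannot be assumed available. And Phase 2 is largely written in the past tense, so a new session item may come too late for this trial.

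The central gap survives: none of these routes is described as asking every child or parent, and DSMB review can only pass on what was recorded.

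**Conclusion.** The point holds as a gap in ascertainment and reporting. No systematic inquiry about reactions to sessions is described, and the SAP has no adverse-event count, denominator or interval. An absence of reports would be compatible with a true rate of up to 10.1% (one-sided 95%, 0 of 28) even if every reaction were captured.

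That 10.1% is a consequence of sample size and remains after any change to the forms, so it should not be read as the cost of passive capture. The part attributable to ascertainment is the increase beyond it: to 13.5%, 20.3% or 40.6% at assumed capture of 75%, 50% or 25%. Those shares are illustrations and nothing in the documents fixes them. The two findings about the text, no described inquiry and no SAP summary, need no assumption. The change is worth making because it is cheap and serves a task the DSMB already has.

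**What to change.** 1. Add one fixed yes/no item to the end-of-session youth form and to the post-intervention survey, asking about upset during the session or since the last one. Keep it apart from the scored usability items so that comparison with the pre-adaptation survey is unaffected. Any yes enters the existing DSMP route; no clinical rule changes.
2. Extend the question to parents through session notes only if the adapted programme kept them.
3. Add to the SAP a table of youth with at least one reaction over all enrolled youth, with an exact 95% confidence interval and a statement of how reactions were ascertained. Give the same table to the DSMB, and settle the denominator (28, or 15 per school).
4. If sessions are complete, report the recorded events with that denominator, state that capture was unsolicited, and carry the item into the efficacy trial.

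The cost is slightly longer forms, one table and a minor IRB modification, similar in kind to the January 2024 request that added the provider form after each session. The count will also look higher than one based on unsolicited reports, which the ascertainment statement should explain.

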Work and Focus Group Discussion. Each group engaged in an interactive discussion and review of each module (adults and youth). Native youth only reviewed 3 modules due to time constraints.

Elder group only: [name] and the project manager asked specific questions about explaining anxiety and depression in a cultural way, what does anxiety and depression mean coming from a cultural context, and what words would you use for anxiety and depression (this added about 60 minutes to their group discussion).

All groups: [name] and the project manager asked specific questions on how content, materials, learning strategies, and delivery methods of the non-adapted PEI program modules could more culturally appropriate or improved, what is not cultural appropriate, and what changes could be made.

At the end of the discussion the facilitators provided a summary of the group's suggestions, invite feedback from participants, and talk about next steps for the project. Adults received a \$40 gift card and youth will receive a \$25 gift card for their participation. Elders will received a \$60 gift card for the additional hour of the work group session.

Youth also completed a usability survey after reviewing each module (3 per focus group) used in previous adaptation studies with Alaskan Native youth (see attached).³⁶ It assessed the likability, acceptability, enjoyable, ease of learning and using skills, credibility, motivational appeal, perceived impact, and cultural appropriateness. The CAB assisted in adapting the items and

rating scale of the useability survey to improve fit for use with 8-12-year-old Native youth from [tribal reservation name].

Cultural Adaption of the PEI Program (Step 3)

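### Does judging the whole programme by each youth's average rating make the 80% acceptability verdict incoherent?

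*Combined protocol and SAP*

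**What the plan says.** The SAP for Phase 2, Study Aim 2, has one numeric success rule for acceptability. It tabulates the "proportion of respondents who rated each module or all modules on average as 2 or 3", and then states: "A module or the entire program was successfully adapted if at least 80% of youth rated it as a 2 or 3". The rule refers to two attributes, acceptability and enjoyability. No confidence interval, error rate or go/no-go decision is attached to the 80%.

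The protocol supplies the structure. Step 3 of the adaptation refers to the "learning objectives of each of the six PEI program modules", although the programme description in the background notes that "Session 6 is a review session". In the Phase 2 section, "The post-adaptation usability survey was administered at the end of each session", so a youth who attends throughout gives six sets of ratings. No separate rating of the whole programme is described.

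The scale's range is not in the text. The Cultural Advisory Board helped adapt the items and the "rating scale of the useability survey to improve fit for use with 8-12-year-old Native youth", and the survey itself was an attachment.

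On numbers, the Phase 2 section says "In Year 3, we recruited 28 Native youth ages 8-12 years-old" and, in the same sentence, "15 youth per school) to participate in the adapted PEI program", which would make 30.

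**The concern.** The same 80% is applied to two different quantities. For a module, a youth counts if the rating is 2 or 3. For the programme, a youth counts if the average over modules is 2 or 3. In an average, a 3 cancels a 1, and a single 1 among 2s pulls a youth below 2. Averages over six modules are also rarely whole numbers: 1.50, 1.67 and 1.83 lie below 2 but round to 2, and the SAP does not say how to class them.

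If this were a defect, the claim that the whole programme was successfully adapted could be made when no module met the rule, or denied when every module met it. A cut-off chosen after seeing the data could decide the result. The suggested cure was to use the pooled share for the programme: all ratings of 2 or 3 divided by all ratings given.

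**Working it through.** The 80% is a chosen threshold, so there is no calculated figure to reproduce.

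**Inputs.** Six modules; 28 youth, or 2 × 15 = 30; pass if the count is at least 0.8 × N, which is 22.4, so 23, of 28, or 24 of 30. Assumed: top score 3, lowest score 1 (0 was also tried), one rating per youth per module, complete data.

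**1. Can the verdicts disagree?** Yes, by hand, with N = 28:

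- Six youth each rate one different module 1; all other ratings are 2. Each module scores 27/28 = 96%. Those six youth average (1 + 5 × 2)/6 = 1.83. The programme scores 22/28 = 79% at average ≥ 2, or 28/28 if averages are rounded.
- Every youth gives three 3s and three 1s, rotated. Each module scores 13 to 15 of 28 (46–54%). Every average is (9 + 3)/6 = 2.0, so the programme scores 100%.
- Seven youth give four 1s and two 2s, and the rest give all 2s. The 7 × 4 = 28 low ratings spread as 4 or 5 per module, so modules score 23 or 24 of 28 (82–86%). The seven average 8/6 = 1.33, so the programme scores 21/28 = 75% under either cut-off.

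With 30 youth the same patterns arise, so the 28-versus-30 discrepancy does not matter here.

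**2. How often?** This depends on rating shares that the documents do not give. Simulation with N = 28, scores 1/2/3 and within-youth latent correlation 0.3 (range over correlations 0 to 0.6 in brackets):

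| Assumed shares of 1/2/3 | Result |
|---|---|
| 10/70/20 | programme passes 21% at ≥ 2, 100% if rounded; all six modules pass but programme fails at ≥ 2 in 54% (27–57%) |
| 10/40/50 | all six pass but programme fails at ≥ 2 in 4.9% |
| 10/30/60 | the same event in about 1% |
| 5/35/60 | the two cut-offs disagree in at most 4.9% of trials over the correlation range |
| 30/20/50 | programme passes 11% at ≥ 2, 97% if rounded; all six fail but programme passes in 1.3% (0.1–14%) at ≥ 2 and 31–52% if rounded |

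The 4.9% in the second row and the 1% in the third are higher at stronger correlation. Disagreement is common when ratings cluster at exactly 2 or, under rounding, when they split between 1 and 3. It is uncommon when ratings are mostly high.

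**3. Would the pooled share be better?** With one rating per module it is a weighted mean of the module shares, so it cannot oppose all of them. Three checks count against it:

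- *Two attributes.* Let every module have 27/28 favourable on acceptability and 20/28 (71%) on enjoyability. If both must reach 80%, all six modules fail, yet the pooled share is (27 + 20)/56 = 47/56 = 84% and passes.
- *Dropout.* Eight of 28 youth rate low and leave after two sessions; 20 rate 3 throughout. Pooled: 120/(120 + 16) = 88.2%, a pass. Share of youth favourable: 20/28 = 71.4%, a fail. The per-youth average gives the 71.4%.
- *Unit.* If all 28 youth give one low rating and five 3s, the pooled share is 5/6 = 83.3%, although no youth rated every module 2 or 3.

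**The case for a change.** The strongest case for a change is that Aim 2 has no other numeric success criterion and that the plan offers no construction of the programme result except the average. In the pattern where each youth gives one 1 and five 2s, every average is 11/6 = 1.83, and the cut-off alone moves the programme from 0% to 100%. The seven-youth example shows that fixing a cut-off does not remove disagreement. The change would cost one sentence and a re-tabulation.

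The arithmetic stands, and so does the observation that the cut-off and the way the two attributes combine are unstated. The inference from disagreement to error does not. Whether a child liked the programme overall and whether each module was liked are separate questions, and two honest summaries may differ. Nor does the programme figure stand alone: Aim 2 also reports attendance, dropout and survey response, the module results are tabulated, and acceptability is explored in focus groups and interviews. A reader would see any disagreement.

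The low cost is also overstated. The SAP section reports its tabulations in the past tense and the ratings are already in hand. In the 10/70/20 illustration the pooled rule would raise the chance of a pass from 21% to 99.8%. Replacing a success rule at that stage, with that effect, is harder to defend than leaving a detail unstated.

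**Conclusion.** No change to the plan follows. It is true that the programme verdict can oppose all six module verdicts, and that fractional averages are not classed. The first is a property of a legitimate per-youth summary. The second, with the unstated combination of acceptability and enjoyability, is missing detail that an analyst would settle sensibly: the plain reading is an unrounded average between 2 and 3, with each attribute shown. Under that reading, disagreement in the illustrations runs mainly towards withholding the programme claim (54% in the 10/70/20 case). The overstating direction had probability 1.3% (0.1–14%) in the 30/20/50 case.

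The pooled share is a trade-off and not a correction. It buys agreement with the modules for a single attribute, but gives up youth as the unit and lets dropout, itself an Aim 2 outcome, reduce the weight of dissatisfied youth. The mismatch between 28 recruited and 15 per school is a clerical matter on this point, since the conclusions are the same at 30.

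The frequencies rest on assumed rating shares, a 1–3 scale, independent youth and complete ratings. The hand-worked examples need only the six modules, a top score of 3 and the stated low scores.
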